2.2 Study Population and Sites

The study will examine the medical records of patients who underwent cardiac surgery in Massachusetts between 1/1/2012 to 12/31/2016. It is estimated that ~50,000 patients are eligible for inclusion in this study. The evaluable sample size is derived from a sample of convenience from the following Institutions.

Baystate Medical Center, Springfield, MA
Beth Israel Deaconess Medical Center, Boston, MA
Brigham and Women's Hospital, Boston, MA
Cape Cod Hospital, Hyannis, MA
SouthCoast Health, Fall River, MA
Massachusetts General Hospital, Boston, MA
Mount Auburn Hospital, Cambridge, MA
UMass Memorial Medical Center-University, Worcester, MA

Tufts Medical Center, Boston, MA

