3.2 Definitions of Covariates

Data derived from individual sites will use definitions from the Society of Thoracic Surgeons Adult Cardiac Surgery Database versions 2.7.3 and 2.8.2 (43,44).

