	Other Previous Cardiac					
57	Interventions	POC	805	-	620	620

	Other previous cardiac					
58	intervention 1	POCInt1	810	-	-	-
	Other previous cardiac					
59	intervention 2	POCInt2	815	-	-	-
	Other previous cardiac					
60	intervention 3	POCInt3	820	-	-	-
	Previous carotid artery					
61	surgery	CVDPCarSurg (1080)	-	1080	557	557
62	Previous ICD	PrOCAICD	-	1460	630	630
63	Previous Pacemaker	PrOCPace	-	1470	640	640
	Previous arrhythmia					
64	surgery	POArr	-	1445	-	-
65	Previous other cardiac	PrOthCar	-	1440	-	-
66	Previous congenital	PrOthCongen	-	1450	621	-
	Previous Aortic Valve					
67	Replacement - Surgical	PrevProcAVReplace	-	1220	-	-
	Previous Aortic Valve					
68	Repair - Surgical	PrevProcAVRepair	-	1230	-	-
	Previous Mitral Valve					
69	Replacement - Surgical	PrevProcMVReplace	-	1240	-	-
	Previous Mitral Valve					
70	Repair - Surgical	PrevProcMVRepair	-	1250	-	-
	Previous Tricuspid Valve					
71	Replacement - Surgical	PrevProcTVReplace	-	1260	-	-
	Previous Tricuspid Valve					
72	Repair - Surgical	PrevProcTVRepair	-	1270	-	-
	Previous Pulmonic Valve					
	Repair / Replacement -					
73	Surgical	PrevProcPV	-	1280	-	-
	Previous Aortic Valve					
74	Balloon Valvuloplasty	PrevProcAVBall	-	1285	-	-
	Previous Mitral Valve					
75	Balloon Valvuloplasty	PrevProcMVBall	-	1290	-	-
76	Previous Transcatheter	PrevProcTCVRep	-	1300	-	-

		Valve Replacement				
		Previous Percutaneous	PrevProc	PercVR	Repai	
77	Valve Repair	r	-	1310	-	-
F. Preoperative Cardiac Status						
79	Previous MI	PrevMI	885	1540	750	750
80	Previous MI - when	MIWhen	890	1550	760	760
81	Prior Heart Failure	PriorHF	920	1590	770	770
82	History of Arrhythmia	Arrhythmia	945	-	840	840
83	History of Arrhythmia	ArrhythWhen	-	1650	-	-
84	VT/VF	ArrhyVtach	-	1660	851	-
		ArrhyVtachSicSinSyn				
85	Sick sinus syndrome	;	-	1680	-	-
86	Third degree heart block	ArrhyTHB	-	1690	852	-
	Second degree heart					
87	block	ArrhyVtachHrtBlk	-	1670	-	-
88	VT/VF	ArrhythVV	950	-	-	-
89	Sick sinus syndrome	ArrhythSSS	955	-	-	-
90	Atrial Flutter	ArrhythAFlutter	960	-	-	-
	Second degree heart					
91	block	ArrhythSecond	965	-	-	-
92	Third degree heart block	ArrhythThird	970	-	-	-
93	Paced rhythm	ArrhythPPaced	975	-	-	-
94	Afib/Aflutter	ArrhythAFib	980	1700	853	-
95	Type of Atrial Fibrillation	ArrhyTyp	-	-	850	850
	Duration of Atrial					
96	Fibrillation	ArrythAFibDur	985	-	-	-
97	Type of Atrial Fibrillation	ArrythAFibTy	-	1701	-	-
G. Preoperative Medications						

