12.2 Figures

Figure 1: CONSORT diagram

Figure 2: Time course of the occurrence of post-discharge AF

Figure 3: Time course of the occurrence of post-discharge stroke stratified by occurrence of post-discharge AF

Figure 4: Time course of the occurrence of post-discharge mortality stratified by occurrence of post-discharge AF

Table 1: Characteristics of the study participants. Data are reported as number and percentage, or median and 10-90% quantiles, as appropriate

CSP = Cardiac surgical program

CHIA = Center for Health Information and Analysis

	Patient characteristic	Data source	Source variable
0	Demographics		
1	Age at surgery (years; N/%)	CSP	Calculated
2	<50		SurgDt - DOB
3	50-59		
4	60-69		
5	70-79		
6	≥80		
7	Gender (Male; N/%)	CSP	Gender
8	Race (Caucasian; N/%)	CSP	RaceCaucasian
9	Ethnicity	CSP	Ethnicity
10	Height (cm; mean/SD)	CSP	HeightCm
11	Weight (kg; mean/SD)	CSP	WeightKg
12	BMI (kg/m ² ; N/%)	CSP	Calculated
13	<20		
14	20-24.9		
15	25-29.9		
16	30-34.9		
17	≥35		
18	Payor		
19	Government	CSP	PayorGov
20	Commercial	CSP	PayorComm
21	HMO	CSP	PayorHMO
22	Prior Medical History		
23	Atrial fibrillation	CSP and CHIA	ArrhythAFib, ArrythAFibDur, ArrythAFibTy
24	Atrial flutter	CSP and CHIA	ArrhythAFlutter
25	History of arrhythmia	CSP and CHIA	
26	Heart block or sick sinus syndrome	CSP and CHIA	ArrhyVtachSicSinSyn, ArrhyTHB, ArrhyVtachHrtBlk, ArrhythSSS

27	VT/VF	CSP and CHIA	ArrhyVtach, ArrhythVV
28	Smoker past or current	CSP	TobaccoUse, CigSmoker, SmokCurr
29	COPD	CSP	ChrLungD
30	Diabetes	CSP	Diabetes, DiabCtrl
31		NIDDM	
32		IDDM	
33	Dyslipidemia	CSP	Dyslip
35	Dialysis	CSP	Dialysis
36	Hypertension	CSP	Hypertn
37	Peripheral vascular disease	CSP	PVD
38	Sleep apnea	CSP	SlpApn
39	Alcohol use	CSP	Alcohol
40	Cerebrovascular disease	CSP	CVD
41	Prior CVA	CSP	CVA, CVAWhen
42	TIA	CSP	CVDTIA
43	Carotid Stenosis	CSP	CVDCarSten
44	Prior carotid surgery	CSP	CVDPCarSurg
45			
46	Medications		
47	ACEI/ARB	CSP	MedACEI48
48	Anticoagulant or anti-platelet drug	CSP	MedACoag
49	Amiodarone	CSP	MedAmiodarone
50	Aspirin	CSP	MEDASA
51	Beta blocker	CSP	MedBeta
52	Calcium channel blocker	CSP	MedCChanTher
53	Antiarrhythmic	CSP	MedAarry
54	Coumadin	CSP	MedCoum
55			
56	Prior Cardiac Status		
57	Heart failure		PriorHF
58	Prior MI		PrevMI, MIWhen
59		Past	
60		Recent	
61	Prior CABG surgery	CSP	PrCAB

62	Prior mitral valve surgery	CSP	PrValveProc1, PrValveProc2, PrevProcMVReplace, PreProcMVRRepair

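### Table 1 row 26 omits the version 2.81 heart-block fields, so its site-derived meaning differs between database versions 2.73 and 2.81

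*Combined protocol and SAP*

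**What the plan says.** Table 1 in Appendix 12 lists, for each baseline characteristic, the data source and the source variables. Row 26 is labelled "Heart block or sick sinus syndrome". Its source is given as both the surgical programs and CHIA, and its variables are "ArrhyVtachSicSinSyn, ArrhyTHB, ArrhyVtachHrtBlk, ArrhythSSS". No CHIA variable or code is named.

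Appendix 9 lists the fields requested from the programs, with the field number each carries in STS versions 2.81, 2.73, 2.61 and 2.52. Among them, on lines 91 and 92, are "ArrhythSecond" (second degree block) and "ArrhythThird" (third degree block). Neither appears in row 26 or anywhere else in Table 1.

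Section 3.2 says that site data follow the definitions of the "Society of Thoracic Surgeons Adult Cardiac Surgery Database versions 2.7.3 and 2.8.2". Section 2.2 sets the cohort as "patients who underwent cardiac surgery in Massachusetts between 1/1/2012 to 12/31/2016". Both version families are thus expected in one cohort, although the documents give no changeover date.

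**The concern.** A pooled covariate should mean the same thing whichever database version recorded the patient. Row 26 takes both heart-block grades from the older version and neither from the newer one, although its label promises heart block throughout. A programmer who follows the shell as written would leave 2.81 heart-block patients out of the site-derived row, and nothing in the output would flag it.

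Both primary aims are to identify risk factors, and section 7.1.1 selects candidates partly on univariate association. A conduction-disease variable that loses cases in one version may be described wrongly in Tables 1 and 2, and may be screened on a definition nobody chose.

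**Working it through.** The plan gives no figure to reproduce. The check sets row 26 against the version columns of Appendix 9.

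**Step 1: field by field**

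| Field | Condition | 2.73 number | 2.81 number | In row 26? |
|---|---|---|---|---|
| ArrhyVtachSicSinSyn (line 85) | Sick sinus syndrome | 1680 | none | yes |
| ArrhyTHB (line 86) | Third degree block | 1690 | none | yes |
| ArrhyVtachHrtBlk (line 87) | Second degree block | 1670 | none | yes |
| ArrhythSSS (line 89) | Sick sinus syndrome | none | 955 | yes |
| ArrhythSecond (line 91) | Second degree block | none | 965 | **no** |
| ArrhythThird (line 92) | Third degree block | none | 970 | **no** |

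ArrhyTHB also has a 2.61 number (852), but section 3.2 does not name 2.61 for this study.

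**Step 2: coverage by version.** Under 2.73 the row covers all three conditions. Under 2.81 it covers one of three. With ArrhythSecond and ArrhythThird added, it covers three of three in both.

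**Step 3: oversight or choice?** Row 26 pairs the old and new sick sinus fields. Row 27 (VT/VF) pairs ArrhyVtach, which has a 2.73 number, with ArrhythVV, which has a 2.81 number. The intention was evidently to harmonise the versions, and two fields were missed.

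**Step 4: how many patients are recorded under 2.81?** The documents do not say. Assume even accrual over the five years 2012 to 2016 and a single changeover t years in. The 2.81 share is s = (5 − t)/5.

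- t = 4: s = 1/5 = 20%
- t = 2.5: s = 2.5/5 = 50%
- t = 1: s = 4/5 = 80%

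**Step 5: what s does and does not measure.** If heart block is equally common in both versions, the share of all heart-block cases missed by row 26 is s × (1 − a) × (1 − c). Here a is the share of block cases that also have sick sinus syndrome, and c is the share of the remainder found through CHIA. The documents give neither a nor c, so s is an upper limit on the share of block cases lost. The share of all patients misclassified is smaller still: that product multiplied by the prevalence of heart block, which is also not given.

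**Step 6: effect on a hazard ratio.** Two things change when block-only patients move to the reference group.

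- The reference group is contaminated. If a share m of it is missed block with hazard ratio HR, an estimate of HR against that group becomes roughly HR/(1 + m(HR − 1)). Assumed values for illustration: m = 1%, HR = 1.5 gives 1.5/1.005 = 1.49; m = 5%, HR = 2.0 gives 2.0/1.05 = 1.90.
- The exposed group shifts towards sick sinus syndrome. If sick sinus syndrome has a larger hazard ratio than block, this raises the pooled ratio. In the limiting case where block has a hazard ratio of 1, the contamination term is 1 + m × 0 = 1, so only the upward shift remains.

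The two can act in opposite directions, and the documents give neither component's effect.

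**The case against.** **CHIA is also a named source.** Appendix 10 includes diagnosis codes among the CHIA fields, so some heart block in 2.81 patients may be found there. A reader might infer that block counts only under 2.73; the documents do not support that, because the yield of CHIA is unknown, not zero. But no code list is given. Even with one, 2.73 patients would have two sources for block and 2.81 patients one, so ascertainment would still differ.

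**The cell could have been cut at a page end.** The missing names are the next conduction fields in Appendix 9 order. However, the list ends without a trailing comma, so truncation is unlikely. A glance at the source page settles it.

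**The version labels do not match.** Section 3.2 says 2.8.2 and the Appendix 9 column says 2.81. That is true, but the plan offers no other field list for the later version.

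**The shell is unfinished elsewhere.** Rows 25, 116, 131 and 141 have no source variable, and row 92 lists a pulmonary field for tricuspid disease. This supports reading row 26 as a slip. It does not make the mapping right: a blank prompts a question, whereas a plausible incomplete list gets programmed.

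**The variable may never enter a model.** This stands. No section commits heart block to a model; it is a candidate subject to selection, and it is neither the main exposure nor an endpoint. That limits the severity.

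**Conclusion.** The mapping is wrong as written. On the listed site fields, row 26 means block or sick sinus syndrome under 2.73, and sick sinus syndrome alone under 2.81. The supported consequences are an artificial version-related drop in prevalence, lost exposed cases and a candidate covariate whose content depends on version.

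Three stronger readings do not hold:

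- **That the conduction-disease hazard ratio must be diluted.** Neither direction nor size can be derived: the exposed group shifts towards sick sinus syndrome, and the contamination illustrated above is small.
- **That 20% to 80% of patients are misclassified.** That range is the possible share recorded under 2.81, given even accrual and an assumed changeover 4 to 1 years in. Only those with heart block, without sick sinus syndrome and not found through CHIA are affected.
- **That the longer follow-up of early patients makes the error worse.** The Cox models handle unequal follow-up by censoring, and the Poisson model in section 7.1.2 uses an offset. The documents show no mechanism by which follow-up length would add to the error.

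This is a minor-to-moderate covariate-mapping error. It should be corrected before programming, but it does not threaten either primary aim's main exposure or endpoint. The finding rests on Appendix 9 being the field list for the later version, and on both versions being present in the cohort, as section 3.2 implies.

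**What to change.** Add ArrhythSecond and ArrhythThird to the source variables of Table 1 row 26, and define the row as any of second degree block, third degree block or sick sinus syndrome in both versions. Tabulate its prevalence, and that of each component, by database version before it is considered for a model. If CHIA is to stay as a source, list the diagnosis codes and apply them identically to patients from both versions.

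The cost is two field names in a shell table and one short tabulation. Both fields are already in the Appendix 9 request, so no new site data are needed.

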7.1.1 Primary Aims

The standard Cox proportional hazards model will be used to model time to first atrial fibrillation occurrence and time to first stroke or other focal neurologic event, after discharge from hospital,

respectively. The potential risk factors included will be selected based on their univariate association with first event status, as well as clinical significance. Hazard ratios with 95% confidence intervals will be reported with a two-sided p-value for statistical significance. The proportional hazard assumption will be evaluated using graphical tool, and by including time dependent covariate terms.

Since there might be repeated occurrences of atrial fibrillation and stroke or other focal neurologic event for each patient, we will use the Andersen-Gill (AG) model and the Prentice, Williams and Peterson (PWP) models to analyze recurrent events data. The AG model is suitable when the interest is in the overall effect on the intensity of the occurrence of a recurrent event. The PWP models allow us to evaluate the effects of risk factors for the kth event after discharge from hospital, as well as the effects of risk factors for the kth event since the time from the previous event (47). Hazard ratios with 95% confidence intervals will be reported with a two-sided p-value for statistical significance. For time-to-event data analyses, death will be considered a censoring event.

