99	ACE inhibitor Use	MedACEI48	1020	1730	900	900
100	Anticoagulant Use	MedACoag	1040	1750	940	940
101	Amiodarone Use	MedAmiodarone	1035	-	-	-
102	Aspirin Use	MedASA	1055	1820	990	990
103	B-blockers <24 hours	MedBeta	1060	1710	890	890
104	B-blockers >2 weeks	MedBetaTher	1065	-	-	-

Calcium Channel						
105	Blocker	MedCChanTher	1070	-	-	-
	Preoperative					
106	Antiarrhythmics	MedAArrhy	-	1770	-	-
107	Coumadin	MedCoum	1075	1780	950	950
108	H. Hemodynamics Cath					
	Number of Diseased					
109	Vessels	NumDisV	1170	1930	1050	1050
110	LV ejection fraction	HDEF	1545	1960	1080	1080
111	Aortic Insufficiency	VDInsufA	1590	2155	1170	1170
112	Aortic Stenosis	VDStenA	1600	2152	1120	1120
113	Aortic Valve Area	VDAoVA	1610	2153	-	-
	Aortic Valve Mean					
114	Gradient	VDGradA	1615	2154	1130	1130
115	Mitral Insufficiency	VDInsufM	1680	2270	1180	1180
116	Mitral Stenosis	VDStenM	1690	2240	1140	1140
	Mitral Valve Mean					
117	Gradient	VDGradM	1705	2260	1180	1180
118	Tricuspid Insufficiency	VDInsufT	1775	2320	1190	1190
119	Tricuspid Stenosis	VDStenT	1785	2300	1150	1150
120	Pulmonary Insufficiency	VDInsufP	1820	2340	1200	1200
121	Pulmonary Stenosis	VDStenP	1840	2330	1160	1160
122	I. Operative (with sections J, K, L and M)					
123	AF procedure	AFibProc	2145	-	2470	2470
124	Afib epicardial lesions	OCarAFibEpLes	4070	-	-	-
125	Afib intracardiac lesions	OCarAFibIntraLes	4105	-	-	-
126	Aortic Arch	AortProcTotArch	4355	-	-	-
127	Aortic Arch	ONCArch	-	-	2530	2530
128	Aortic Arch	ONCArch	-	5480	-	-
129	Aortic Hemi-arch	AortProcHemi	4350	-	-	-
130	Aortic Procedure	AortProc	2150	-	-	-
131	Aortic Procedure	OpAortic	-	-	1630	1630
132	Aortic Procedure Type	OCAoProcType	-	5471	-	-
133	Aortic Root	AortProcRoot	4340	-	-	-

134	Aortic Root	ONCAoRt	-	5473	-	-
135	Aortic Valve Procedure	VSAVPr	-	4280	-	-
136	Aortic Valve Surgery	VSAV	3390	4270	-	-
	Arrhythmia Correction					
137	Surgery	OCarACD	-	5400	-	-
	Arrhythmia Correction					
138	Surgery Lead Extraction	OCarACDLI	-	5410	-	-
139	Arrythmia device	OCarACD	4085	5400	2450	2450
140	Ascending Aorta	AortProcAsc	4345	-	-	-
141	Ascending Aorta	ONCAsc	-	-	2520	2520
142	Ascending Aorta	ONCAsc	-	5474	-	-
143	ASD-PFO repair	OCarASD		5240	-	-
144	ASD-PFO repair	OCarASDPFO	4075	-	-	-
	Atrial Appendage					
145	Procedure	OCarAAProc	4080	-	2480	2480
	Atrial Fibrillation					
146	Ablation Procedure	OCarAFibAProc	-	5465	-	-
	Atrial Fibrillation Surgical					
147	Procedure	OCarAFibSur	-	5450	-	-
148	CABG performed	OpCAB	2120	2437	1280	1280

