63	Prior other valve surgery	CSP	PrValveProc1, PrValveProc2, PrevProcAVReplace , PrevProcAVRepair , PrevProcTVReplace , PrevProcTVRepair , PrevProcPV , PrevProcAVBall , PrevProcMVBall , PrevProcTCVRep , PrevProcPercVRepair
64	Other cardiac surgery	CSP	PrOthCar, PrOthCongen, POC, POCInt1, POCInt2, POCInt3
65	Prior ICD placement	CSP	PrOCAICD
66	Prior pacemaker placement	CSP	PrOCPace
67	Prior arrhythmia surgery	CSP	POArr
69			
70	Preoperative laboratory testing		
77	White cell count (10^6 /dL)	CSP	WBC
78	Creatinine (mg/dL)	CSP	CreatLst
79			
80	Preoperative Cardiac Imaging		
81	Number of diseased coronary vessels	CSP	NumDisV
82	0		
83	1		
82	2		
83	≥ 3		
84	LV Ejection fraction	CSP	HDEF
85	<30%		
86	30-54%		
87	$\geq 55\%$		
88	Aortic stenosis	CSP	VDStenA
89	Aortic insufficiency	CSP	VDInsufA
90	Mitral stenosis	CSP	VDStenM
91	Mitral insufficiency	CSP	VDInsufM
92	Tricuspid valve disease	CSP	VDStenT, VDStenP
93	Pulmonary valve disease	CSP	VDStenP, VDInsufP

94

95 **Surgery**

[figure not shown]
96	Year of operation	CSP	SurgDt
97		2012	
98		2013	
99		2014	
100		2015	
101		2016	
101	CABG surgery	CSP	OpCAB
102	Number of conduits placed	CSP	DistArt + DistVein
103		1	
104		2	
105		>=3	
106	AVR surgery	CSP	VSAVPr, VSAV
107	MVR surgery	CSP	OpMitral, VSMVPr, VSMV
108	Other valve surgery	CSP	OpPulm, VSPV, OpTricus, VSTV
109	Ascending aortic surgery	CSP	AortProcTotArch, ONCArch, AortProcHemi, AortProc , OpAortic, OCAoProcType, AortProcRoot, ONCAoRt, AortProcAsc, ONCAsc, ONCAsc
110	Other non-CABG, non valvular surgery	CSP	OpOCard
111	Atrial septal surgery	CSP	OCarASD, OCarASDPFO
114	Ventricular outflow tract surgery	CSP	OCarSubaStenRes , ResectSubA
115	Congenital heart surgery		OCarCong , OCarCongProc1 , OCarCongProc2 , OCarCongProc3
116	Carotid endarterectomy	CSP	
117	Reoperation	CSP	Incidenc
118	Surgical urgency	CSP	Status
119		Elective	
120		Urgent	
121		Emergent	
122	Postoperative duration (days)	CSP	DischDt - SurgDt
123			
124	Post-operative complications		

125	Stroke	CSP and CHIA	CNSTrokP
126	TIA	CSP and CHIA	CNSTrokTTIA
127	Atrial fibrillation	CSP and CHIA	COAtFib
128	Reoperation for bleeding	CSP and CHIA	COpReBld
129	Pacemaker inserted	CSP and CHIA	CRythmDis
130	In-hospital atrial fibrillation	CSP	COAtFib
131	In-hospital atrial flutter	CSP	
132			
133	Discharge medications and devices		
134	Aspirin	CSP and CHIA	DCASA
135	Warfarin	CSP and CHIA	DCCoum
136	Anti-platelet agent	CHIA	-
137	Beta blocker	CSP and CHIA	DCBeta
138	Amiodarone	CSP and CHIA	DCAmiodarone

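### Table 1 row 92 builds tricuspid valve disease from a pulmonary stenosis variable and omits the collected tricuspid insufficiency variable

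*Combined protocol and SAP*

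**What the plan says.** Section 12, Table 1, gives a data source and source variables for most characteristics. Row 92, "Tricuspid valve disease", comes from the surgical programs and lists "VDStenT, VDStenP". Row 93, for pulmonary valve disease, lists "VDStenP, VDInsufP".

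Appendix 9 is the list of fields requested from the programs and serves as the dictionary. It labels VDStenT (line 119) as "Tricuspid Stenosis" and VDStenP (line 121) as "Pulmonary Stenosis". Line 118 lists VDInsufT as the tricuspid insufficiency field, with a field number in each of the four STS versions shown (1775, 2320, 1190, 1190).

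On how covariates reach the Cox models, section 7.1.1 says: "The potential risk factors included will be selected based on their univariate association with first event status, as well as clinical significance". Section 7.1.2 selects covariates for the Poisson models in a similar way. Neither section names tricuspid disease.

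**The concern.** Row 92 pairs one tricuspid field with one pulmonary field, so the label and the content do not match. Tricuspid insufficiency is requested from every site and then not used in the table.

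Both primary aims are to determine risk factors, and section 1.2 itself links AF with valvular disease beyond the mitral valve. Tricuspid disease is therefore a plausible candidate for the models. A candidate built from the wrong fields could fail the univariate screen when it should pass. It could also pass and carry an estimate that does not describe tricuspid disease. Whatever the models select, the descriptive tables would report a figure under the wrong label.

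The slip is easy to miss. VDStenP is a valid field name, so code written from row 92 would run without an error.

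**Working it through.** The plan has no figure to reproduce here. The check compares Table 1 with Appendix 9 and then follows the rule through.

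**Step 1: valve-disease rows of Table 1 against the dictionary.**

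| Table 1 row | Label (paraphrased) | Listed variables | Meaning in Appendix 9 | Match? |
|---|---|---|---|---|
| 88 | Aortic stenosis | VDStenA | aortic stenosis | yes |
| 89 | Aortic insufficiency | VDInsufA | aortic insufficiency | yes |
| 90 | Mitral stenosis | VDStenM | mitral stenosis | yes |
| 91 | Mitral insufficiency | VDInsufM | mitral insufficiency | yes |
| 92 | Tricuspid disease | VDStenT, VDStenP | tricuspid stenosis, pulmonary stenosis | **no** |
| 93 | Pulmonary disease | VDStenP, VDInsufP | pulmonary stenosis, pulmonary insufficiency | yes |

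Row 92 is the only valve-disease row that takes a field from another valve. It is also the only combined row without an insufficiency field. VDStenP feeds two differently labelled rows, and VDInsufT feeds none. The neighbouring rows read cleanly, so a fault in text extraction is unlikely.

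**Step 2: is the mapping corrected elsewhere?** Section 3.2 points to STS definitions, which cover the raw fields and not this composite. Section 3.3 deals with admissions and diagnosis codes. Section 5 has a title and no text. Row 92 is the only stated derivation.

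**Step 3: consequence of the rule.** Assume that a patient counts as having the disease when any listed field is positive. The documents do not state this rule. Write T for tricuspid stenosis, I for tricuspid insufficiency and P for pulmonary stenosis. Row 92 as written is (T or P); the row that fits its label is (T or I).

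| T | I | P | As written | Fits label | Result |
|---|---|---|---|---|---|
| 1 | any | any | yes | yes | agree |
| 0 | 1 | 0 | no | yes | missed |
| 0 | 0 | 1 | yes | no | wrongly included; also in row 93 |
| 0 | 1 | 1 | yes | yes | agree, but only through the pulmonary field |
| 0 | 0 | 0 | no | no | agree |

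Two patterns are misclassified, in opposite directions. The error in the reported count is therefore

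reported − correct = n(P only) − n(I only),

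where each n counts patients with that lesion alone among the three. The two errors partly cancel in the total, so a believable total would not show that the row is sound. The documents give neither n, so neither the size nor the sign of the net error can be computed.

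**Step 4: route to the models.** Under section 7.1.1 the variable is used only if it is selected on univariate association and clinical significance. Bias in a model therefore depends on that selection, and on the analyst using the row 92 mapping.

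**The case against.** The strongest reply is that this is a clerical slip in a descriptive shell. The same column has other slips against Appendix 9: several misspelt field names, one field listed twice in row 109, and rows 25, 116 and 131 with no source variable. The row label, row 93 and the dictionary all show what was meant. The correct field is being collected, and an analyst who checked row 92 against Appendix 9 would see the mismatch. Most of this stands, and it is why the point is minor and is an inconsistency and not a methodological choice. It does not remove the point. A misspelt name matches nothing and is caught, whereas VDStenP matches a real field.

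Two stronger readings are tempting, and the documents do not support them.

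- A reader might infer that the hazard ratio for tricuspid disease, and the adjustment of the primary models, are wrong as planned. Tricuspid disease is not a named covariate, and no section says that the models must use the Table 1 definitions. The analyst could enter the raw fields. The bias is conditional.
- A reader might infer that every patient with isolated tricuspid insufficiency will be coded as disease-free and every patient with isolated pulmonary stenosis as diseased. That presumes an any-positive rule. The column is a list of source fields; other rows mix a condition with a qualifier (for example CVA with CVAWhen), and no threshold is given for any valve field.

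**Conclusion.** The mismatch is certain: row 92 lists a pulmonary stenosis field under a tricuspid label, leaves out tricuspid insufficiency, and is not corrected elsewhere. Followed as written, it gives a wrong tricuspid line in Table 1. It does the same in Table 2 if that table carries the same characteristics, as section 6.4 suggests; the rows of Table 2 are not printed.

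The effect on the AF and stroke models is possible but not established, because it requires the variable to be selected with this mapping. The direction of any resulting bias cannot be settled from the documents. The number of patients affected is unknown. Prior AF as exposure, all endpoints, the negative-control plan and the power statement in section 4 do not depend on this row. Minor, but worth correcting before the derivations are programmed.

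**What to change.** In Table 1 row 92, replace VDStenP with VDInsufT, so that the source variables are VDStenT and VDInsufT. This follows the stenosis-plus-insufficiency pattern of row 93. Use the same mapping for Table 2 and for any model that includes the covariate.

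Changing the field name corrects the source list but still does not say when a patient counts as having the disease. A short note giving the rule for combining the two fields, and the grade that counts as present, would complete the definition; row 93 needs the same note.

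The cost is one cell and, with the note, one or two sentences. No new data are needed, because both fields are already on the Appendix 9 list.

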1.1 Study Introduction

Briefly, this study examines the occurrence and neurological consequences of atrial fibrillation, occurring after discharge to home or rehab after cardiac surgery. The study examines patients who underwent cardiac surgery at Cardiac Surgical Programs in Massachusetts between 1/1/2012 and 12/31/2016, with a follow-up period that extends to 12/31/2017.

Detailed data will be obtained from individual Programs that encompasses preoperative medical history, the operative period including details about the operation and also the post-operative period until discharge from hospital. Information about the post-hospital discharge course for individual patients will be obtained from the Massachusetts Center for Health Information and Analysis (CHIA) (<https://www.mass.gov/orgs/center-for-health-information-and-analysis>). CHIA collects detailed financial and patient-level data from Massachusetts payers and providers, and makes it available to researchers.

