2.4 Secondary Aims

The Secondary Aims of this study are to determine:

1. The frequency of, and treatments for, atrial fibrillation occurring after discharge from hospital in patients who underwent cardiac surgery during admission.
2. The frequency of stroke or other focal neurologic event occurring after discharge from hospital in patients who underwent cardiac surgery during admission
3. The incidence of all-cause and stroke-related mortality after cardiac surgery.

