197	Date of Death	MtDate	5030	6400	3060	3060
198	Primary cause of death	MtCause	5040	6420	3080	3080
199 R. Discharge (with Section S)						
200	Aspirin	DCASA	5060	6460	3120	3120
201	Warfarin	DCCoum	5085	6510	3180	3180
202	Antiarrhythmic	DCArhy	-	6440	3100	3100
203	Antiarrhythmic name	DCArMN	-	-	3110	3110
204	Readmission	Readm30	-	6550	3220	3220
	Primary readmission					
205	reason	ReadmRsn	-	6560	3230	3230
206	Amiodarone	DCAmiodarone	5110	-	-	-
207	Beta-blocker	DCBeta	5105	6480	3140	3140
208	Discharge location	DisLoctn	5045	6520	3190	3190

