139			
140	Post-discharge atrial fibrillation		
141	Discharged in AF	CSP	
142	1 - 30 days	CHIA	
143	31 - 90 days	CHIA	
144	91 - 182 days	CHIA	
145	183 - 365 days	CHIA	
146	1 - 2 years	CHIA	
147	2 - 3 years	CHIA	
148	3 - 4 years	CHIA	
149	4 - 5 years	CHIA	
150			
151	Post-discharge stroke		
152	1 - 30 days	CHIA	
154	31 - 90 days	CHIA	
155	91 - 182 days	CHIA	
156	183 - 365 days	CHIA	
157	1 - 2 years	CHIA	
158	2 - 3 years	CHIA	
159	3 - 4 years	CHIA	

160	4 – 5 years	CHIA
161		
162	Mortality	
163	30-day mortality	CSP
164	1-year mortality	CSP
165	5-year mortality	CSP

Table 2: Comparison of characteristics of patients with post-discharge atrial fibrillation and those patients who did not have post-discharge atrial fibrillation

Figure 1: CONSORT Diagram.

Patients reported in local STS databases (N = xx,xxx)

Operations reported local STS databases (N = xx,xxx)

Excluded after matching

- x,xxx patients
- x,xxx operations

Patients reported remaining after matching (N = xx,xxx)

Operations reported remaining after matching (N = xx,xxx)

Excluded after data review (N=x,xxx)

- Inclusion criterion not present
- Exclusion criterion present
- Covariate data not present
- Missing outcome

Eligible patients (N = xx,xxx)

CABG-only surgery (N = xx,xxx)

AVR +/- CABG surgery (N = xx,xxx)

MVR +/- AVR +/- CABG surgery (N = xx,xxx)

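### One-year and five-year mortality are sourced to surgical-program data described as ending at discharge, and no source is named for later out-of-hospital deaths or their causes

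*Combined protocol and SAP*

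**What the plan says.** **Scope of each source.** Section 1.1 describes the program data as covering preoperative history, "the operative period including details about the operation and also the post-operative period until discharge from hospital". The same section says that the course after discharge comes from CHIA.

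**Table 1 (Section 12).** The rows for post-discharge AF and stroke by interval follow that split and cite CHIA. The mortality rows do not: 30-day mortality, "1-year mortality" and "5-year mortality" all cite the programs (CSP), with no source variable.

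**Death fields.** Section 9 lists three surgical-database items: mortality, date of death and "Primary cause of death". No time window is given for any of them. The CHIA list in Section 10 (items a to m) has no vital status, date of death, cause of death or discharge disposition. Section 8.1 says that the final analytic data set holds no CHIA case mix fields.

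**Where death is used.** Secondary Aim 3 is "The incidence of all-cause and stroke-related mortality after cardiac surgery". Section 7.1.2 plans logistic models for both outcomes, and Table 5 and Figure 4 report post-discharge mortality. Section 7.1.1 states: "For time-to-event data analyses, death will be considered a censoring event". Section 7.1.2 uses length of follow-up as the Poisson offset.

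**The concern.** A source described as ending at discharge does not by that description supply vital status at one or five years, and the source given the later period has no listed death field. Two things are at stake.

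- **The mortality endpoint.** Deaths at home, in hospice or in another facility, beyond about 30 days, would be missed, and so would their causes. Stroke-related mortality depends on cause and is the more exposed of the two outcomes.
- **The AF and stroke analyses.** Censoring at death requires knowing that the patient died. An unseen death leaves the patient in the risk set, event-free, until the administrative end on 12/31/2017, and adds the same false time to the Poisson offset. If prior-AF patients die faster, their event rate is diluted more and the main comparison moves toward the null. Section 1.2 makes that direction plausible, since it reports higher mortality with preoperative AF.

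**Working it through.** **The plan's own figure.** The only computed figure is the Section 4 effect size. With 4,000 v 46,000 patients, h = (1.960 + 0.842) × √(1/4000 + 1/46000) = 0.0462, which agrees with the stated 0.046. The present point does not affect it. The plan gives no figure for mortality or person-time.

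**Follow-up from the stated dates.** Surgery runs from 1/1/2012 to 12/31/2016 and follow-up ends on 12/31/2017. Potential follow-up C is therefore 1 to 6 years, with mean 3.5 if accrual is uniform (an assumption).

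**Person-time if no post-discharge death is seen.** With a constant death hazard λ, true mean time is the average of (1 − e^(−λC))/λ over C uniform on 1 to 6:

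T(λ) = 1/λ − (e^(−λ) − e^(−6λ)) / (5λ²)

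For λ = 0.05: 20 − (0.9512 − 0.7408)/0.0125 = 3.17 years. The documents give no death hazards, so every λ below is an assumption.

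| λ per year | T(λ), years | Overstatement, 3.5/T | Dilution, T/3.5 |
|---|---|---|---|
| 0.03 | 3.29 | 1.06 | 0.941 |
| 0.04 | 3.23 | 1.08 | 0.923 |
| 0.05 | 3.17 | 1.105 | 0.905 |
| 0.08 | 2.99 | 1.17 | 0.854 |
| 0.10 | 2.88 | 1.22 | 0.823 |

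**Effect on a true rate ratio of 2.0 (prior AF v none).**

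- Hazards 0.03 v 0.08, none captured: 2.0 × 0.854/0.941 = 1.81.
- Hazards 0.04 v 0.10, none captured: 2.0 × 0.823/0.923 = 1.78.
- Half of deaths captured: the observed time is the average of 3.5 and T, so dilution becomes T/(1.75 + T/2). The factors are 0.970 and 0.921 for the first pair, and 0.960 and 0.903 for the second. The ratio reads 2.0 × 0.921/0.970 = 1.90 and 2.0 × 0.903/0.960 = 1.88.

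**The Cox model.** I simulated the first-event model with 8% prior AF, an assumed AF hazard of 0.08 per year without prior AF, a true hazard ratio of 2.0, and deaths independent of AF within group. With follow-up run to the administrative end, the hazard ratio reads 1.80 and 1.75 for the two pairs. Censoring at death recovers 2.0. The bias in the primary model is therefore about the same size.

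**A one-year window.** True time is (1 − e^(−λ))/λ: 0.985 and 0.961 for the first pair, 0.980 and 0.952 for the second. Even with no death captured, the rate ratio reads 2.0 × 0.961/0.985 = 1.95 and 2.0 × 0.952/0.980 = 1.94.

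**A related limit.** Only patients operated on in 2012 can have five full years by 12/31/2017. That is 366 of 1,827 accrual days, or 20%, so five-year mortality cannot be a simple whole-cohort proportion even if every death is known.

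**The case against.** The fair reply is that the plan is under-specified rather than unworkable, and much of that stands.

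- Discharge as the limit of program data rests on one summary sentence. The date-of-death field has no stated window, and the program list includes a 30-day readmission item. In-hospital deaths, and perhaps 30-day deaths, may well be available.
- The Section 10 list is described only as the least needed for the merge. Table 1 takes discharge anti-platelet agents from CHIA, although no such field is on that list, so CHIA evidently supplies more. Deaths during a readmission may be among it.
- Follow-up time is not undefined, because an administrative end date is given. Only its earlier end at death lacks a source.
- The 1.8 figure assumes that no post-discharge death is seen. That is the extreme case.

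A reader might infer that late mortality cannot be obtained at all, or that the primary aims are invalid. The documents support neither. They show a conflict over the source and a missing specification, and even the extreme case is an attenuation of roughly 10% toward the null.

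The reply does not close the gap. No section says where an out-of-hospital death after about 30 days, or its cause, would be recorded.

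**Conclusion.** The concern holds in this limited form: Table 1 conflicts with Section 1.1, and no named source covers late out-of-hospital deaths or their causes. Followed as written, the plan would under-count Secondary Aim 3, Table 5 and Figure 4 by an amount that cannot be estimated from the documents.

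The effect on the AF analyses is indirect and bounded. Person-time is overstated by at most 6% to 22% over the assumed hazards, and a true ratio of 2.0 reads about 1.8 with no late death captured or about 1.9 with half captured. These sizes rest on assumed constant death hazards, uniform accrual and faster death in the prior-AF group. If the two groups died at the same rate, the Poisson ratio would not be diluted, although the absolute rates would still be too low.

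**What to change.** 1. Reconcile Sections 1.1, 8.1 and 10 with Table 1, and correct the Table 1 source for mortality. Name the source and field for post-discharge death and for its cause.
2. If there is no such source, restrict and rename the mortality endpoint, Table 5 and Figure 4 to recorded deaths: the index stay, 30 days if the field's window is confirmed, and deaths during CHIA encounters if a discharge-status field is confirmed. Do not report 1-year, 5-year or stroke-related mortality as complete.
3. State in the primary analyses that unobserved deaths leave patients at risk, and in which direction this may bias the estimates.
4. Add a sensitivity analysis with a short fixed follow-up window, for example one year, where unseen deaths matter least. Do not censor at the last CHIA encounter: AF and stroke are detected through those encounters, so that censoring is informative.

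**Cost.** Naming a source is a wording change if the field is already held, and a new linkage if it is not. The fallback costs a narrower mortality claim, and the sensitivity analysis is a small amount of extra work.
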